6.3 Availability

MUC1 100mer peptide and Poly-ICLC will be supplied by the University of Pittsburgh and sent to each participating site's research pharmacy upon receipt of a completed CPN Study Agent Order Form. The vaccine/saline placebo injection will be prepared by each participating organization's pharmacy (or other appropriate designated personnel) within 8 hours prior to clinical administration. Normal saline for placebo injection will be provided by each participating organization. Study agent will be supplied by and shipped from:

[name]., [name]
[contact]; [contact]; E-mail: [contact]

6.4 Agent Distribution

Agent will only be distributed to participating organizations after documentation of IRB approval of the DCP-approved protocol and consent is provided to DCP, collection of all Essential Documents is complete (see DCP website for description of Essential Documents), and Drug Shipment Authorization has been confirmed.

6.5 Agent Accountability

The Investigator, or a responsible party designated by the Investigator, must maintain a careful record of the inventory and disposition of all agents using NCI Drug Accountability Record Form (DARF) or comparable institutional form. The investigator or designee is required to maintain adequate records of receipt, dispensing, and final disposition of study agent. Include on receipt record from whom the agent was received and to whom study agent was shipped, date, quantity, and batch or lot number. On dispensing record, note quantities and dates study agent was dispensed to and returned by each participant.

After receipt of the final site close out visit report by the CPN Compliance Coordinator, any remaining study agent may be destroyed per institutional guidelines.

Forms required for study agent ordering, accountability, and return are available on the CPN website: <http://cancerpreventionnetwork.org>

6.6 Packaging and Labeling

Participating site pharmacy personnel will not be blinded to the study intervention. However, the pharmacy personnel will be required to label the injection supplied for each participant in such a manner as to not provide any information about intervention assignment to the site investigators. Each injection should be labeled according to institutional guidelines. The label should define the injection as MUC 1 100mcg/0.05mL w. poly-ICLC 500mcg/0.25mL or placebo 0.3mL. The label should also include the date of preparation, the route of administration, and the study name. The label may also include other information, such as the time of expiration, if required by local or state regulations.

6.7 Storage

The MUC-1 vaccine will be stored frozen at -70 to -80° C until mixed for injection. MUC1 Vaccine will be shipped on dry-ice overnight to each site. Participating organizations are required to store the vaccine in a -70 to -80° freezer upon receipt.

Poly-ICLC is stable at room temperature for brief periods (days). It is normally refrigerated at about 40°F (2-8°C) but should not be frozen. Poly-ICLC will be shipped at ambient temperature overnight to each participating site. It is to be stored in the refrigerator upon receipt.

6.8 Pre-Registration and Registration/Randomization

6.8.1 Participant Pre-Registration

6.8.1.1 To pre-register a participant, access the Cancer Prevention Network (CPN) web page (<https://cancerpr.ipower.com/member/MAY2013-01-01.shtml>) and enter the remote pre-registration application. The remote pre-registration application is available 24 hours a day, 7 days a week. Back up and/or system support contact information is available on the Web site. If unable to access the Web site, call the CPN Registration Office at [contact] between 8:00 a.m. and 4:30 p.m. Central Time (Monday through Friday).

The instructions for remote pre-registration are available on the CPN web page (<https://cancerpr.ipower.com/member/MAY2013-01-01.shtml>) and detail the process for completing and confirming participant pre-registration. Prior to initiation of protocol screening, this process must be completed in its entirety and a CPN Participant ID number (PID) must be available as noted in the instructions. It is the responsibility of the individual pre-registering the participant to confirm the process has been successfully completed. Participant pre-registration via the remote system can be confirmed in any of the following ways:

- Contact the CPN Registration Office [contact]. If the participant was fully pre-registered, the Registration Office staff can access the information from the centralized database and confirm the pre-registration.
- Refer to “Instructions for Remote Pre-Registration” in section “Finding/Displaying Information about a Registered Participant” within the Remote Registration/Randomization User’s Manual available for download from the CPN website.

6.8.1.2 At the time of pre-registration, the following will also be verified:

- IRB approval at the registering institution
- Participant eligibility (including existence of a signed informed consent document)
- Existence of a signed authorization for use and disclosure of protected health information (USA Institutions only).
- Study agent is available and Drug Shipment Authorization has been granted to the registering site.
- The following will also be recorded:
 - Participant has/has not given permission to collect and store blood and/or tissue for future use in research to learn about, prevent, treat, or cure cancer.
 - Participant has/has not given permission to collect and store blood and/or tissue for future use in research about other health problems (for example: Barrett’s esophagus. causes of diabetes mellitus, Alzheimer’s disease, and heart disease).
 - Participant has/has not given permission to send blood and/or tissue sample(s) to researchers at an outside institution.
 - Participant has/has not given permission to his/her doctor (or someone from the Cancer Prevention Network) to contact them in the future to ask them to take part in more research.

6.8.1.3 Baseline (screening) evaluations must be completed within the guidelines specified on the Schedule of Events (See Section 7.1).

6.8.1.4 Registration Office personnel will automatically register participants separately to the translational components of the study (See Section 13).

6.8.2 Registration/Randomization

6.8.2.1 Fax to [contact] a completed Eligibility Checklist (see CRF packet) to the CPN Registration Office between 8:00 a.m. and 4:30 p.m. Central time, Monday through Friday.

6.8.2.2 Randomization: For details, see Section 13.2.

6.8.2.3 Intervention on this protocol must commence at a CPN institution under the supervision of a CPN clinician.

6.8.2.4 Intervention cannot begin prior to Registration/Randomization and must begin \leq 14 days after Registration/Randomization.

6.8.2.5 Pathology and colonoscopy reports confirming diagnoses must be sent \leq 30 days post Registration/Randomization to the CPN QAS at CPN Operations Office, [name]; or [contact], Attention CPN QAS.

6.8.2.6 Once the intervention assignment has been ascertained by the CPN Registration Office, the appropriate blinded study agent information (MUC1 vaccine or placebo/saline injection) will be communicated to the designated data manager/nurse/pharmacist at the participant's Participating Organization. The name of this contact person is to be entered in the designated space on the eligibility checklist so the Registration Office personnel have it for each participant at the time of registering/randomizing the participant. Make sure this contact person will be available at the time of the registration so he or she can receive the information from the Registration Specialist. This contact person may not be involved in assessing adverse events or any other outcome measure and should not be the same person listed on page one of the eligibility checklist form as the person completing the form. The last page of the eligibility checklist form should provide the source of communication for the contact person, either fax or email, and the appropriate contact information.

6.8.2.7 Stratification Factors:

- Number of advanced adenoma on qualifying colonoscopy: ≥ 3 vs. < 3
- Gender: male vs. female

After the participant has been registered on to the study, values of the stratification factors will be recorded. Randomization will be performed by CPN personnel. The CPN electronic-based randomization system will be utilized to ensure that randomization of participants to appropriate study arms while balancing the stratification variables is carried out successfully.

6.9 Blinding and Unblinding Methods

There are two distinct situations in which it will be deemed appropriate to break the randomization assignment for participants enrolled onto this current trial:

- In the event of an *emergency* for an individual participant.
- Serious Adverse Event (SAE) that fulfills the criteria for expedited reporting to the FDA.

In these situations, Participating Organization personnel may assume the participant is on active agent and call the CPN Registration Office within one business day to receive unblinding information. The study name/number, participant identifier, and participant initials will be required to break the randomization code. The Participating Organizations are responsible for notifying the medical monitor at DCP, NCI of the unblinding event.

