3.2 Study Design

This is a randomized, double-blind, placebo controlled phase II trial designed to elicit immune responses to abnormal MUC1. A 1-year booster vaccine will be administered to assess the presence of T cell dependent immune memory. Participants will be randomized on a 1:1 scheme. The protocol will call for injections at week T0, T2, and T10, and a booster injection at week T53. Monitoring of the immune response will be at each time point prior to injection, T0, T2, T10 and at week T12, T52, T55 (post booster), and at the time of the endpoint surveillance colonoscopy up to T156, for a total of 7 measurements of MUC1 immune response. For details regarding study visits and assessments, see Section 7.

Up to 120 participants will be approached for pre-registration, and assuming an 8% ineligibility rate, approximately 110 participants will be randomized to either vaccine or placebo injections and followed up to 3 years for the primary and secondary endpoints. A dropout rate of up to 10% is assumed between baseline and year 1, and an additional 10% drop out rate is assumed between year 1 and year 3 (termination of follow-up).

Eligible participants will have had an advanced adenoma that was completely resected as reported by endoscopic assessment. Advanced adenomas will be defined as: 1) ≥ 1 cm in size; 2) demonstrates villous or tubulovillous histology; or 3) have severe or high grade dysplasia. We anticipate enrolling approximately 4 participants per month across all sites for the first 3-6 months, and then 8 participants per month across all sites until we reach the accrual target. Accrual is expected to be completed in 18 months. Total study duration for Part 1 is expected to be about 22 months, followed by an additional 12 months for Part 2 and 24 months for Part 3.

Intervention Arms: Participants meeting study criteria will be randomly assigned to receive one of two interventions according to the following intervention schedule:

- Muc1/poly ICLC 0.3 mL subcutaneous study vaccine in the upper thigh
- Normal saline injection 0.3 mL subcutaneous in the upper thigh

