11.2.2 Reporting SAEs to DCP

11.2.2.1 The Lead Organization and all Participating Organizations will report SAEs on the DCP SAE form found at http://prevention.cancer.gov/files/clinical-trials/SAE_form.doc.

11.2.2.2 Contact the DCP Medical Monitor by phone within 24 hours of knowledge of the event.

[name] [name], FACS
National Institutes of Health, National Cancer Institute
Division of Cancer Prevention
[name]
[name]
[contact]
Fax (with cover sheet, Attn: Dr. [name]): [contact]
Email (preferred): [contact]

Include the following information when calling the Medical Monitor:

- Date and time of the SAE
- Date and time of the SAE report
- Name of reporter
- Call back phone number
- Affiliation/Institution conducting the study
- DCP protocol number
- Title of protocol
- Description of the SAE, including attribution to drug and expectedness

11.2.2.3 The Lead Organization and all Participating Organizations will FAX or email written SAE reports to the DCP Medical Monitor within 48 hours of learning of the event using the paper SAE form.

The written SAE reports will also be FAX'ed or emailed to [name], Study Principal Investigator and CCS Associates, DCP's Regulatory Contractor.

[name].
Email: [contact]
[contact]

DCP's Regulatory Contractor, CCS Associates:
Email: [contact]
[contact]

Participating Sites will also FAX this form to the CPN Operations Office within 48 hours of learning of the event at [contact]. See the Data Management Plan (see CPN web site) sections "Data Collection" and "Data Entry and Processing" for further instructions as SAEs must also be recorded on the participant's appropriate case report forms.

11.2.2.4 The DCP Medical Monitor and regulatory staff will determine which SAEs require FDA submission, per CFR 21 Section 312.32

11.2.2.5 The Lead Organization and all Participating Organizations will comply with applicable regulatory requirements related to reporting SAEs to the IRB/IEC.

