13.7.1 Adverse Event Stopping Rule

The trial will be monitored closely for occurrence of adverse events by the study team and by the Mayo Clinic Cancer Center Data Safety and Monitoring Board (DSMB) using the adverse event (AE) stopping rule specified below during the first 2 parts of the study (i.e. first 57 weeks):

Adverse Event Stopping Rule: The stopping rule specified below is based on the knowledge available at study development. We note that the Adverse Event Stopping Rule may be adjusted in the event of either (1) the study re-opening to accrual after any temporary suspension or (2) at any time during the conduct of the trial and in consideration of newly acquired information regarding the adverse event profile of the treatment(s) under investigation. The study team in consultation with the Mayo DSMB may also choose to suspend accrual because of unexpected adverse event profiles that have not crossed the specified rule below.

Accrual will be temporarily suspended to this study if at any time we observe events considered at least possibly related to study treatment (i.e., an adverse event with attribute specified as "possible", "probable", or "definite") that satisfy any of the following criteria for each arm separately:

- If at any time 2 of the initial 10 treated participants or 20% of all participants (i.e. when accrual is greater than 10 participants) have experienced a grade 3 or higher adverse event.)
- Each grade 5 event will be reviewed on a case by case basis in a real time fashion to determine whether study accrual should be suspended. We will also review all grade 4 adverse events regardless of attribution to monitor the emergence of any previously unrecognized treatment related adverse event.

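### Section 6.9 lets site staff learn the arm for SAEs meeting FDA expedited-reporting criteria, with no rule that causality be recorded first or that assessors stay blinded

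*Combined protocol and SAP*

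**What the plan says.** Section 3.2 sets the design: "This is a randomized, double-blind, placebo controlled phase II trial". Section 6.9 names two situations in which the code may be broken. One is an emergency for an individual participant. The other is a "Serious Adverse Event (SAE) that fulfills the criteria for expedited reporting to the FDA". In both, site personnel are permitted to "call the CPN Registration Office within one business day to receive unblinding information". The sponsor's part is to be told: "The Participating Organizations are responsible for notifying the medical monitor at DCP, NCI of the unblinding event". No prior approval is stated.

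Section 11.2.2 governs SAE reporting. A phone call to the DCP Medical Monitor is due within 24 hours and must cover attribution and expectedness. A written report follows within 48 hours. The decision on FDA submission rests with the sponsor: "The DCP Medical Monitor and regulatory staff will determine which SAEs require FDA submission, per CFR 21 Section 312.32". No time limit is set for it. Section 11.1.2 makes attribution a required adverse event data element, without tying it to the time of any unblinding.

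For the site contact who receives the assignment at randomization, 6.8.2.6 is strict: "This contact person may not be involved in assessing adverse events or any other outcome measure".

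Section 13.7.1 then uses attribution as a gate: "Accrual will be temporarily suspended to this study if at any time we observe events considered at least possibly related to study treatment". The events counted are grade 3 or higher, within each arm separately. The limit is 2 of the first 10 treated, or 20% once accrual passes 10. Section 13.7 defines toxicities by the same three categories of relatedness (possible, probable, definite).

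**The concern.** Causality is a judgement, and knowing the arm can influence it. An assessor who learns that a participant received saline has reason to call the event unrelated; one who learns that it was vaccine has reason to call it at least possible. The stopping rule counts only related events and counts them by arm, so such a shift would raise the vaccine count and lower the placebo count. The secondary comparison of toxicity between arms would move in the same direction.

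Section 6.9 leaves three things open: who at the site may hear the code, whether the site waits for DCP's decision, and whether the causality rating is recorded before the call. The protocol takes care over this separation at randomization and is silent on it here. Patient care does not depend on this second route, because the emergency route stands on its own.

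**Working it through.** The plan states no error rate or operating characteristic for unblinding or for the stopping rule, so there is no figure to reproduce. The check has two parts.

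**1. The sections side by side**

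| Question | Text | Result |
|---|---|---|
| Who receives the code? | 6.9: site personnel | No limit by role |
| Who decides that an SAE goes to FDA? | 11.2.2.4: DCP Medical Monitor and regulatory staff | 6.9 does not tell the site to wait |
| When is attribution first due? | 11.2.2.2: 24-hour phone report | Not placed before the unblinding call |
| Can attribution change later? | 11.1.2: CRF element | No lock and no flag for changes |
| Must an unblinded person stay out of adverse event assessment? | 6.8.2.6: yes, for the designated contact | 6.9 has no counterpart |

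A site that phones DCP first and waits has already given a blinded attribution. The exposure arises in three cases, all of which the text allows: the site judges the criteria itself, it calls for the code before phoning DCP, or it completes or revises the CRF attribution after learning the arm.

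**2. How far the early trigger depends on attribution**

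From the plan: n = 10 treated in an arm, trigger at 2 counted participants. Let p be the probability that a participant has a counted event. Then

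P(2 or more of 10) = 1 − (1 − p)^10 − 10p(1 − p)^9.

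The documents give no p, so the following are assumptions:
- q: proportion of participants per arm with a grade 3 or higher event (5%, 10%, 20%).
- b = 0.5: proportion of those events rated at least possibly related when blinded.
- f: fraction of those events unblinded before rating.
- Once unblinded, every vaccine event is rated related and no placebo event is. This is the extreme case.

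For vaccine p = q[b(1 − f) + f]; for placebo p = q·b(1 − f). With q = 10% and f = 0, p = 5% and P = 1 − 0.5987 − 0.3151 = 8.6%. With f = 0.10, p is 5.5% for vaccine and 4.5% for placebo.

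| q | Blinded, each arm | f = 0.10 (vaccine / placebo) | f = 0.25 | f = 0.50 | f = 1 |
|---|---|---|---|---|---|
| 5% | 2.5% | 2.9% / 2.0% | 3.7% / 1.4% | 5.2% / 0.7% | 8.6% / 0% |
| 10% | 8.6% | 10.1% / 7.2% | 12.6% / 5.2% | 17.0% / 2.5% | 26.4% / 0% |
| 20% | 26.4% | 30.3% / 22.5% | 36.1% / 17.0% | 45.6% / 8.6% | 62.4% / 0% |

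Only SAEs that meet expedited criteria are open to this route, so a low f is the more natural reading. The pilot described in 2.3 saw nothing above grade 1, which argues for a low q. After the first 10, the limit grows with the arm: 20% of 20 is 4 participants, and 20% of 55 is 11.

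**The case against.** The strongest reply is that 6.9 and 11.2.2 can be read in sequence: the site phones in the SAE with its attribution, DCP decides on submission, and only then may the code be broken. Section 6.9 does not say when its one business day begins, so nothing in it contradicts this order. That stands, and it defeats some stronger readings.

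- A reader might infer that attribution is not due until the 48-hour written report. It is due in the 24-hour call.
- A reader might infer that the site is forced to pre-empt DCP's decision. The wording is permissive; the site may do so but need not.
- A reader might infer that 6.9 contradicts 6.8.2.6. That clause binds only the contact designated at randomization. The two sections differ in strictness and do not contradict each other.

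There are also backstops. Section 13.7 provides for review of grade 3 to 5 events judged unrelated or unlikely to be related. Section 13.7.1 provides for review of grade 4 events whatever their attribution and of grade 5 events case by case. It also allows accrual to be suspended for unexpected profiles that have not met the rule, and the suspension is temporary. Section 12.4 points to a Master DSMP that is not among the documents and might set an order.

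What survives is narrower. The sequential reading is possible but not required by the text, and the backstops do not replace the attribution-based count that triggers suspension.

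**Conclusion.** The gap is real and minor. As written, the person rating causality may know the arm when making or revising the rating. This is inconsistent with the separation applied to the designated contact in 6.8.2.6, and both the by-arm stopping rule and the toxicity definition depend on that rating.

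The likely effect is small. At f = 0.10 and q between 5% and 10%, the early trigger probability moves by at most 1.5 percentage points in either arm (8.6% to 10.1%, and 8.6% to 7.2%). The large shifts in the table need every event to be unblinded before rating and every rating then to follow the arm; nothing in the documents supports that. The event rates, the blinded rate of relatedness and the direction of the shift are all assumptions.

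A reader might also infer that any one unblinded SAE can decide a suspension. That holds only if the event is grade 3 or higher, its rating changes between unrelated and at least possibly related, and the arm's count is otherwise one short of its limit. For the limit of two, the participant must be among the first 10 treated in that arm. The primary endpoint is a laboratory ELISA ratio and is not directly affected.

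**What to change.** Amend 6.9 as follows.

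- Leave the emergency route unchanged.
- For expedited reporting, have the CPN Registration Office release the code only to the DCP medical monitor and regulatory staff, after the site's dated attribution is on record and DCP has made its 11.2.2.4 determination.
- State that site staff who assess adverse events stay blinded unless the emergency route applies.
- Flag to the DSMB any change of attribution made after the code was released.

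The cost is wording in 6.9 and a flag for changed attributions. The 24-hour and 48-hour deadlines do not move, and no new staff are needed.
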